17. SAFETY

- **Adverse Events and Laboratory Abnormalities**

- **Adverse Events**

An AE is any untoward medical occurrence in a patient or clinical investigation subject who has been enrolled in a clinical study and who may have been given an investigational product, regardless of whether or not the event is assessed as related to the study treatment. An AE can therefore be any unfavorable and unintended sign (including an abnormal laboratory finding), symptom, or disease temporally associated with the use of an investigational product, regardless of whether or not the event is assessed as related to the investigational product. Pre-existing medical conditions that worsen during a study should be recorded as AEs. Abnormal laboratory values, ECG findings, or vital signs are to be recorded as AEs if they meet the criteria described in Section 3.3.

All untoward events that occur after informed consent through 30 days after the decision to discontinue study treatment (or the date the subject is deemed to be a screen failure) are to be recorded by the investigational site. This requirement includes AEs from unscheduled as well as scheduled visits.

Assessment of the relationship of the AE to the study treatment by the investigator is based on the following two definitions:

- Not Related: A not-related AE is defined as an AE that is not associated with the study treatment and is attributable to another cause or there is no evidence to support a causal relationship;
- Related: A related AE is defined as an AE where a causal relationship between the event and the study treatment is a reasonable possibility. A reasonable causal relationship is meant to convey that there are facts (eg, evidence such as dechallenge/rechallenge) or other clinical arguments to suggest a causal relationship between the AE and study treatment.

- **Serious Adverse Events**

The SAE definition and reporting requirements are in accordance with the International Conference of Harmonisation (ICH) Guideline for Clinical Safety Data Management: Definitions and Standards for Expedited Reporting, Topic E2A.

An SAE is defined as any untoward medical occurrence that at any dose:

- Result in death;
- Is immediately life-threatening (ie, in the opinion of the investigator, the AE places the subject at immediate risk of death; it does not include a reaction that, had it occurred in a more severe form, might have caused death);
- Requires inpatient hospitalization or results in prolongation of an existing hospitalization;
- Results in persistent or significant disability or incapacity:
 - Note: The term “disability” refers to events that result in a substantial disruption of a subject’s ability to conduct normal life function.
- Is a congenital anomaly or birth defect;
- Is an important medical event (IME):
 - Note: The term “important medical event” refers to an event that, based upon appropriate medical judgment, may not be immediately life-threatening or result in death or hospitalization, but may jeopardize the subject or require intervention to prevent one of the other serious outcomes listed under the definition of SAE. Examples of IMEs include intensive treatment in an emergency room or at home for allergic bronchospasm; blood dyscrasias, or convulsions that do not result in hospitalization; or development of product dependency or product abuse.

▪ Serious Adverse Event Reporting

As soon as an investigator becomes aware of an AE that meets the definition of ‘serious,’ this should be documented to the extent that information is available.

- Investigator shall notify sponsor within twenty-four (24) hours of making such discovery by submitting a completed SAE report form and any other pertinent SAE information as indicated on the SAE reporting form;
- Written IND safety reports will be submitted to the FDA by the IND sponsor, for serious, unexpected suspected adverse reactions within 15 calendar days of learning of its occurrence. If the event is fatal or is deemed to be life threatening, the report will be made within 7 calendar days. The IND sponsor will also make an assessment of whether the event constitutes an unanticipated problem posing risks to subjects or others (UP). This assessment will be provided to the Emory University IRB, which, in turn will make

a final determination. If the Emory IRB determines an event is a UP it will notify the appropriate regulatory agencies and institutional officials.

- For multicenter studies the Investigator must notify the IND/CTA Sponsor by submitting a completed SAE report form and any other pertinent SAE information as indicated on the SAE reporting form within 24 hours to allow the IND/CTA Sponsor to submit the SAE report form to Exelixis no later than 2 business days.
- This report must be submitted by sponsor to Exelixis at e-mail: [contact] or [contact], even if it is not felt to be drug related;
- Pregnancy (for a subject or for the partner of a subject), although not itself an SAE, should also be reported on a pregnancy form and be followed up to determine outcome, including spontaneous or voluntary termination, details of birth, and the presence or absence of any birth defects or congenital abnormalities;
- SAEs that must be recorded on an SAE Reporting form include the following:
 - all SAEs that occur after informed consent and through 30 days after the decision to discontinue study treatment (or the date the subject is deemed to be a screen failure);
 - any SAEs assessed as related to study treatment or study procedures, even if the SAE occurs more than 30 days after the decision to discontinue study treatment;
 - although most hospitalizations necessitate reporting of an SAE, some hospitalizations do not require SAE reporting, as follows: elective or previously scheduled surgeries or procedures for pre-existing conditions that have not worsened after initiation of treatment (eg, a previously scheduled ventral hernia repair); pre-specified study hospitalizations for observation; or events that result in hospital stays of fewer than 24 hours and that do not require admission (eg, an emergency room visit for hematuria that results in a diagnosis of cystitis and discharge to home on oral antibiotics). SAEs must, however, be reported for any surgical or procedural complication resulting in prolongation of the hospitalization.

- **Regulatory Reporting**

All serious unexpected adverse drug reactions (unexpected related SAEs) must be reported to all appropriate regulatory authorities, Emory IRB, and Ethics Committees by the investigator as required by 21 CFR 312.32 or by Directive 2011/20/EC:

- These reports are to be filed utilizing the Form FDA 3500A (MedWatch Form) or a CIOMS-1 form;
- The final MedWatch Form or CIOMS-1 form must be submitted by the sponsor to Exelixis within one to two business days of submission to the FDA or applicable regulatory agency (including confirmation of date that the report was submitted) to allow Exelixis time to cross-report to Exelixis' IND. E-mail: [contact]; [contact].
- Exelixis reserves the right to upgrade the Investigator assessment of an SAE based on Sponsor reporting responsibilities.

- **Other Safety Considerations**

- **Laboratory Data**

All laboratory data required by this protocol and any other clinical investigations should be reviewed. Any abnormal value that leads to a change in subject management (eg, dose reduction or delay or requirement for additional medication or monitoring) or that is considered to be of clinical significance by the investigator should be reported as an AE or SAE as appropriate.

- **Pregnancy**

If a subject becomes pregnant during the study, she will be taken off study treatment and will be followed through the end of her pregnancy. The investigator must inform the Sponsor of the pregnancy. Forms for reporting pregnancies will be provided to the study sites upon request. The outcome of a pregnancy (for a subject or for the partner of a subject) and the medical condition of any resultant offspring must be reported to Exelixis or designee. Any birth defect or congenital anomaly must be reported as an SAE, and any other untoward events occurring during the pregnancy must be reported as AEs or SAEs, as appropriate.

- **Medication Errors/Overdose**

Any study drug administration error or overdose that results in an AE, even if it does not meet the definition of serious, requires reporting within 24 hours to Exelixis or designee.

- **Follow-Up of Adverse Events**

Any related SAEs or any AEs assessed as related that led to treatment discontinuation, including clinically significant abnormal laboratory values that meet these criteria, ongoing 30 days after the decision to discontinue study treatment must be followed until either resolution of the event or determination by the investigator that the event has become stable or irreversible. This follow-up guidance also applies to related SAEs that occur *> 30 days after the decision to discontinue* study treatment. The status of all other continuing AEs will be documented as of 30 days after the decision to discontinue study treatment.

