3.3 Cabozantinib Dose Modifications, Interruptions, and Discontinuation

Subjects will be monitored for AEs from the time of signing informed consent through their last follow-up visit (30 days after the date of the last dose of cabozantinib treatment.) Subjects will be instructed to notify their physician immediately at the onset of any AE. Causality assessment of AEs will be determined by the investigator. AE severity will be graded by the investigator in accordance with CTCAE v.4.0.

The following should be taken into consideration in decisions regarding dose modifications (reductions or interruption):

- As a general approach all AEs should be managed with supportive care at the earliest signs of toxicity considered related to the study treatment. Should this be ineffective, dose interruptions and/or reductions should be considered to prevent worsening of toxicity.
- Dose modification criteria for cabozantinib are shown in Table 3-3. Dose interruptions and/or reductions should be implemented for unacceptable toxicity. Doses may be modified at any time while a subject is on treatment.

The assigned starting dose for cabozantinib is 40 mg/day. 1 dose reduction level of cabozantinib is permitted to 20 mg/day (see Table 3-2).

- Dose reductions or interruptions may also occur in the setting of lower grade toxicity than defined in Table 3-3, if the investigator feels it is in the interest of a subject's safety and will optimize drug tolerability.
- Interruption of cabozantinib treatment for cabozantinib-related AEs may occur at any time per investigator discretion. If treatment is interrupted due to related AEs for more than 6 weeks, cabozantinib should be discontinued unless there is unequivocal evidence that the subject is benefitting. In this situation, a subject may be able to restart therapy with a dose reduction upon resolution of the toxicity per the discretion of the investigator.
- Dose interruptions for reason(s) other than related AEs (eg, surgical procedures) can be longer than 6 weeks per the discretion of the investigator.

Table 3-2: Dose Reductions of Cabozantinib

Guidelines for the management of specific AEs are provided in Section 3.3.2.

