AEs associated with pembrolizumab exposure, including coadministration with additional compounds, may represent an immunologic aetiology. These immune-related AEs (irAEs) may

occur shortly after the first dose or several months after the last dose of pembrolizumab/combination treatment and may affect more than one body system simultaneously. Therefore, early recognition and initiation of treatment is critical to reduce complications. Based on existing clinical study data, most irAEs were reversible and could be managed with interruptions of pembrolizumab/combination treatment, administration of corticosteroids and/or other supportive care. For suspected irAEs, ensure adequate evaluation to confirm etiology or exclude other causes. Additional procedures or tests such as bronchoscopy, endoscopy, skin biopsy may be included as part of the evaluation.

- Diabetes mellitus: Type 1 diabetes mellitus has occurred (including diabetic ketoacidosis). Monitor closely for hyperglycemia and other signs/symptoms of diabetes. Insulin therapy may be required; if severe hyperglycemia is observed (Grade 3), administer antihyperglycemics and withhold pembrolizumab treatment until glucose control has been accomplished.
- Gastrointestinal toxicity: Immune-mediated colitis has occurred, including cases of grade 2 to 4 colitis. The median time to onset of colitis was 3.4 months (range: 10 days to ~10 months) and the median duration was 1.4 months (range: 1 day to ~7 months) in patients with melanoma. In patients with NSCLC, the median time to onset was 1.6 months (range: ~1 to ~2 months) and the median duration was 16 days (range: 1 to ~6 weeks). In some melanoma patients, colitis was managed with high-dose systemic corticosteroids for a median duration of 6 days (range: 1 day to 5.3 months), followed by a corticosteroid taper. Most patients with colitis experienced complete resolution. May require treatment interruption, systemic corticosteroid therapy, and/or permanent discontinuation. Monitor for signs and symptoms of colitis; administer systemic corticosteroids for grade 2 or higher colitis.

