	Pre-therapy (Day -14 to 0)	Day 1 of each cycle (21 days) while on study drugs ⁿ	30 - 37 Days after last dose	At one year ^b	End of follow up at 2 years ^b
History and Physical	X	X	X (and every 3 months) ^b	X	X
Weight and ECOG PS	X	X	X (and every 3 months) ^b	X	X
Tumor Measurement	X ^a	X (every 9 weeks)		X ^m	
CBC and diff ^d	X	X ^c	X (and after 3 months)	X	X
Chemistries (Na, CL, CO2, K, BUN, blood glucose ^e Creatinine, Ca, Mg, Phos), Urine analysis	X	X ^{c,e}	X (and after 3 months)	X	X
Liver function panel ^f	X	X ^c	X (and every 3 months)	X	X
PT, PTT, INR	X	X ^c	X	X	
TSH	X	X ^c	X (and every 3 months)	X	X
12-lead ECG	X ^l	X ^l			
Tissue for Research Purposes (paraffin embedded) ^g	X				
Blood for Research Purposes	X ^k				
Toxicity Assessment ^h	X	X			
Radiology: CT-neck, chest, abdomen, and pelvis for tumor measurements ⁱ	X	X (every 9 weeks)		X	
Blood or Urine B-HCG ^j	X				

^a.a range of 4 days before or after the scheduled scans and screening tests is allowed – for scans , a 28 days period is allowed to obtain scans before initiation of therapy)

^b. Once the patient has fully recovered from the study drug-related toxicities or the patient enrolls in a hospice, the follow up can be done by a phone call if the patient is off the study drugs.

^cLaboratory testing will be performed every 3 weeks for the first 9 weeks followed by assessments every 6 weeks. CBC with diff, liver function panel and blood chemistries (excluding T3, T4, TSH, GGT, LDH, Amylase, Lipase; PT, PTT/INR) will continue to be done every 3 weeks with each new cycle following the first 9 weeks of therapy.

^d. CBC and diff includes: WBC, ANC, HCT, HGB, PLT, % lymphocytes, % monocytes, % neutrophils, other Differential (labs need to be done within 7 days of start of therapy)

^{sea}

^e. GGT, Amylase, Lipase, LDH can be performed every 3 cycles

^f. Liver function panel includes: Alk Phos, Total Bilirubin, SGOT (AST), SGPT (ALT), Total Protein.(Labs need to done within 7 days of start of therapy)

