^m Only for select patients who have lack of prior progression at one year

ⁿ- A 2 days window for infusion of Pembrolizumab is allowed for logistic reasons- Every effort should be made to avoid interruption in Cabozantinib administration as a result of changes in Pembrolizumab schedule. A 2 day window for clinical labs and history & physical is also allowed for logistical reasons.

If the subject is unable to have a study assessment taken within the defined time window due to an event outside of his or her control (eg, clinic closure, personal emergency, inclement weather, vacation), the assessment should be performed as close as possible to the required schedule.

Regular tumor assessments should be performed in accordance to the guidelines in Section o to determine if PD is present.

The Treatment Period ends when a subject receives his or her last dose of study treatment; the subject then enters the Post-Treatment Period.

○ **Post-Treatment and End on Treatment Period**

Subjects will return to the study site 30 to 37 days after their last dose of cabozantinib, pembrolizumab or both to complete end-of-study assessments.

At the end of 24 months of treatment on the combination of pembrolizumab and cabozantinib, patients who are in continued response and who in the opinion of the investigators can continue to benefit from therapy will be given the options of either terminating therapy, or continuing on the combination with the use of the EASE program overlooked by Exelixis ; This program will provide commercial cabozantinib to patients who wish to continue therapy for an additional 12 months of treatment; patients who continue on the EASE program will be followed as per standard of care at the respective institutions.

Laboratory and physical examinations will be performed. Remaining study treatment will be returned by the subject, and treatment compliance will be documented. Additional follow-up will occur for subjects with AEs related to study treatment that are ongoing at the time of this visit, and for subjects with SAEs related to study treatment that occur after the time of this visit.

○ Laboratory Assessments

Laboratory panels are composed of the following:

Hematology	
 • WBC count with differential (including at minimum: neutrophils, basophils, eosinophils, lymphocytes, monocytes) • hematocrit • platelet count • RBC count • hemoglobin • ESR • reticulocytes

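### Non-serious adverse events that start more than 30 days after the decision to stop treatment have no clear recording requirement, although late immune-related events are expected

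*Combined protocol and SAP*

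**What the plan says.** Section 17 (Adverse Events) sets the general recording rule: "All untoward events that occur after informed consent through 30 days after the decision to discontinue study treatment". Its SAE reporting and AE follow-up rules count from the same decision. Section 3.3 uses another starting point: AE monitoring runs to a last follow-up visit placed "30 days after the date of the last dose of cabozantinib treatment". Section 16 (Post-Treatment and End on Treatment Period) puts the end-of-study visit 30 to 37 days after the last dose of cabozantinib, pembrolizumab or both.

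Two rules reach past the window. Section 17 (Serious Adverse Event Reporting) also requires "any SAEs assessed as related to study treatment or study procedures, even if the SAE occurs more than 30 days" after the decision to stop, and Section 16 provides follow-up "for subjects with SAEs related to study treatment that occur after the time of this visit". Separately, Section 16 (Laboratory Assessments) and Section 17 (Laboratory Data) make a laboratory abnormality that changes management an AE entry, with no end date. For what remains, Section 17 (Follow-Up of Adverse Events) says: "The status of all other continuing AEs will be documented as of 30 days after the decision to discontinue study treatment".

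The pembrolizumab warnings in Section 3.4.1 state that immune-related events may "occur shortly after the first dose or several months after the last dose of pembrolizumab/combination treatment". Table 16-1 schedules history and physical, liver panel and TSH at 30 to 37 days, then every 3 months, and at 1 and 2 years. Its "Toxicity Assessment" row is marked only before therapy and on Day 1 of each cycle.

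**The concern.** Further defining the toxicities of the regimen is a secondary objective (Section 2.1), and Section 18 assesses safety from AEs. The protocol expects some immune toxicity to appear late and schedules contacts at which it could be found, but it does not clearly tell sites to record such an event if it is non-serious.

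The loss may not be recoverable at analysis. Section 25 (Case Report Forms) keeps physical examination and laboratory results in source documents only. Section 3.4.2 stops concomitant medication recording 30 days after the last dose. A late non-serious event without an AE entry may therefore leave no trace in the database, including through the drugs used to treat it.

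The differing start points add a second problem: the length of AE observation after the last dose can vary between patients for administrative reasons.

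**Working it through.** The plan states no figure to reproduce, and no power or error-rate calculation bears on the point. The check sets the rules side by side and then counts days.

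**Rules for an event that starts after treatment**

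| Type of event | Where | Recording ends |
|---|---|---|
| Any AE | Section 17, Adverse Events | 30 days after the decision to stop |
| Any AE (monitoring) | Section 3.3 | 30 days after last cabozantinib dose |
| Related SAE | Section 17, SAE Reporting | No limit |
| Laboratory abnormality that changes management | Section 16, Laboratory Assessments; Section 17, Laboratory Data | None stated |
| Toxicity assessment | Table 16-1 | Day 1 of last cycle |

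A late related SAE is covered. A late laboratory abnormality that changes management is covered if the laboratory rule overrides the 30-day limit, which is not stated. A late non-serious event that is not a laboratory finding, such as a rash or arthritis, falls under no rule after the window. Footnote h of Table 16-1 does not fill the gap, because it follows to resolution only toxicities that arose during treatment.

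**Day counts, with day 0 as the last dose of both drugs**

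1. Decision on day 0: the Section 17 window closes on day 0 + 30 = 30. The end-of-study visit is on days 30 to 37. An event starting on days 31 to 37 and found at that visit is outside the window.
2. Decision after a hold: assume 0 to 42 days, from the 6-week interruption limit in Section 3.3. The Section 17 window closes between day 0 + 30 = 30 and day 42 + 30 = 72. The Section 3.3 window closes on day 30 throughout. The two can differ by up to 72 − 30 = 42 days.
3. First 3-monthly contact: the table does not say where the 3 months start. Taking 3 months as 90 days, the contact falls on day 90 if counted from the last dose, or on day 30 + 90 = 120 to 37 + 90 = 127 if counted from the end-of-study visit.
4. Gap between window closure and that contact: at least 90 − 72 = 18 days and at most 127 − 30 = 97 days. The contact falls after the window in every case considered, as do those at 1 and 2 years.

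A non-serious, non-laboratory event that starts after the window and is found at any of these contacts therefore need not be recorded.

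**The case against.** The strongest defence is that a 30-day window for all AEs with an unlimited tail for related SAEs is a coherent choice. The trial is small and single-arm, it lists AEs, and it has no safety hypothesis after the run-in. The SAE definition includes important medical events, so some late severe immune events would qualify without hospitalisation. This stands. A reader might infer that delayed toxicity as a whole goes unrecorded; the SAE rule contradicts that.

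The laboratory rule also weakens the obvious examples. A late TSH or liver-enzyme rise that needs treatment or closer monitoring fits its wording. This stands in part. Section 17 (Adverse Events) refers abnormal laboratory values to the criteria in Section 3.3, where monitoring ends at 30 days, so sites could read the rule either way. It would not clearly cover non-laboratory events.

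A reader might also infer that pembrolizumab is left out of the window altogether. That goes too far: Section 17 refers to study treatment in general, and Section 16 names both drugs for the end-of-study visit. Only Section 3.3 ties the window to cabozantinib alone.

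Finally, the numbers may be small. Applying the single-agent incidences in Section 3.4.1 to 34 patients gives 0.07 × 34 = 2.4 to 0.08 × 34 = 2.7 with hypothyroidism, 0.02 × 34 = 0.7 to 0.04 × 34 = 1.4 with pneumonitis, and at most 0.02 × 34 = 0.7 with colitis. These cover events at any time, and the late non-serious share cannot be derived from them. They argue for modest weight but do not remove the gap.

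**Conclusion.** The point holds in limited form. Non-serious AEs, including immune-related ones, that start after the window have no clear recording requirement, and the rules on the start of the window and on laboratory abnormalities do not agree. Followed as written, the plan would under-count late non-serious toxicity for a secondary objective. The primary endpoint and the run-in DLT decision, which uses the first cycle, are unaffected.

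The size is unknown. A reader might try to infer it from the onset medians in Section 3.4.1 and the 6-month PFS of 23% in Section 1.1. The documents do not support that. Several of the later medians come from melanoma patients, and others are early (hepatitis 26 days; hyperthyroidism 1.4 to 1.8 months). None says what share of events began after stopping. The PFS figure is for pembrolizumab alone and does not give the distribution of stopping times for the combination.

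The day counts assume that both drugs end on the same day, a hold of 0 to 42 days before the decision, and 90 days for 3 months. The recording gap itself does not depend on these assumptions. This is a cheap improvement to make, not a flaw that undermines the trial.

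**What to change.** - Reconcile Sections 3.3, 16 and 17 to one anchor for AE and SAE recording and for the end-of-study visit: the last dose of either study drug. Let the window run through the actual date of the 30 to 37 day visit.
- State how long the laboratory-abnormality rule in Sections 16 and 17 applies, consistent with that window.
- Mark Toxicity Assessment in Table 16-1 at the 30 to 37 day visit and at the existing 3-monthly contacts, by phone where footnote b allows.
- Record treatment-related and immune-related AEs of any grade at least to the first 3-monthly contact, together with the start date of any new anticancer therapy.

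No visits are added and no treatment rule changes. The cost is some extra CRF entries, and attribution becomes harder once a patient has started another therapy; the recorded start date allows those events to be shown separately. Phone contacts will yield less than clinic visits, because they provide no examination or laboratory result.
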